### **4. Study Design**

RABBIT-SpA is a prospective observational cohort study. The rules of good pharmacoepidemiological practice are followed [24]. Physicians aiming at taking part in RABBIT-SpA must sign a contract with the DRFZ. The aim is to observe each patient for at least five years, if possible, for ten years.

Patients enrolled will have the following visits: baseline, months 3, 6, 12, 18, 24, 30, 36, 42, 48, 54, 60. If the patient agrees, the observation will be prolonged with visits at 66, 72, 78, 84, 90, 96, 102, 108, 114 and 120 months.

There is no influence on any treatment decision from the principal investigators, scientific advisory board or pharmaceutical companies sponsoring the study. The type of the treatment administered, and the conduct of individual therapy is determined by the treating physician only.

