## **7.2 Events of interest**

In agreement with all companies funding RABBIT-SpA, a number of “events of interest” which require specific attention were defined. They are:

- tuberculosis
- other serious infections (e.g. pneumonia, infections of the CNS, septicemia, bone or joint infections, opportunistic infections)
- congestive heart failure
- myocardial infarction
- stroke
- central demyelination
- serious hematologic disorders (e.g. bone marrow depression and hypoplastic anemia)
- neoplasms (lymphomas, solid malignancies, other neoplasms)
- serious systemic hypersensitivity reactions / serious infusion reactions
- hepatic failure
- serious gastrointestinal ulcer/perforation
- Crohn's disease
- colitis ulcerosa
- uveitis
- pregnancies
- deaths
- reversible posterior leucoencephalopathy syndrome (RPLS)
- renal failure
- progressive multifocal leukoencephalopathy
- Stevens Johnson syndrome (SJS) /toxic epidermal necrolysis (TEN)
- suicidal ideation/behavior
- interstitial lung disease (ILD)

Frequencies and crude incidence rates of these events of interest will be reported regularly (see 7.4). Changes of the list above have to be based on an agreement between the pharmaceutical companies funding RABBIT-SpA and the principal investigators.

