#### **7.4 Six monthly reports**

Every six months each pharmaceutical company funding RABBIT-SpA will receive a report which contains detailed records on each particular SAE (events of interest and other SAE) which occurred during the 6 months period and which were assigned to their index drug in the licensed indications covered by this registry. The report comprises also all SAEs assigned to control treatments. Except for deaths and malignancies an SAE is assigned to all index drugs a patient received during the last 3 months before the onset of the SAE (3-months risk window). SAEs which cannot be assigned to one of the index drugs according to this rule are assigned to control treatment. This approach with equal risk windows for different drugs will be used for feasibility reasons. In contrast, malignancies and deaths will be assigned to all treatments the patient was ever exposed to during the observation in RABBIT-SpA. The assignments are not connected with a conclusion about a causal relationship.

In addition to the detailed reports of SAEs the companies funding RABBIT-SpA will receive summary reports comprising crude cumulative incidence rates of events of interest and their 95% confidence intervals for their own drugs and for the control groups. The so called "Manchester template" is used to report the event rates. This "Manchester template" was defined and harmonized between the British, Swedish and German RABBIT biologics register and includes incidence rates of the total number of all observed SAEs.

Detailed multivariate analyses cannot be provided every six months, but will be done in scientific investigations and published in international journals.

Furthermore, summary reports of non-serious AEs assigned to an index drug of the company will be contained in the six months reports. If required by the respective company, these AEs will be grouped into mild, moderate, or severe AEs.

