## **8. Statistical analysis**

### **8.1. Safety endpoints**

One aim of RABBIT-SpA is to protect future patients from harm caused by serious adverse events. It is impossible to achieve this aim by following a pre-specified list of primary hypotheses since the spectrum of possible SAEs is wide and every list would therefore be incomplete. New scientific results or new agents may lead to extensions and/or changes in the list of “events of interest”. Therefore, the principal investigators and the study physician are free to decide which safety concern will be investigated next.

There is no general statistical analysis plan which would be appropriate for the different scientific questions. For different AEs different confounders have to be considered. Patients follow up for several years will likely receive changing treatments. These changes have to be taken into account. Furthermore, the decision to prescribe, to stop or to continue a treatment depends on the availability of treatment options and experiences with these alternatives. For this reason the mix of patients receiving a particular treatment may change during follow-up. The risk of developing an AE may therefore change over time for various reasons (see below). Possible confounding factors or biases have to be taken into account to avoid any false conclusion. In RABBIT-SpA this will be done by considering the following principles of statistical safety analyses:

Principles of the statistical analysis for publications

a) Confounding by indication will be taken into account

Treatment decisions are based on the needs of a particular patient. Patients treated with new targeted therapies (index treatments) will be more severely ill and have more treatment failures than patients treated with standard therapies. For this reason comparisons based on crude unadjusted estimates cannot be interpreted adequately. In all publications from RABBIT-SpA appropriate statistical methods that are able to account for confounding by indication have to be applied.

b) Patient characteristics which likely influence the risk of developing a particular AE will be taken into account.

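### Section 7.4 sets no before-onset limit for malignancies, so read literally a cancer can be counted against a drug first started after its diagnosis

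*Protocol*

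**What the plan says.** Section 7.4 sets two assignment rules in the same paragraph. For serious adverse events other than deaths and malignancies, "an SAE is assigned to all index drugs a patient received during the last 3 months before the onset of the SAE". By way of contrast, "malignancies and deaths will be assigned to all treatments the patient was ever exposed to during the observation in RABBIT-SpA". The first rule names onset as its reference point. The second names only the observation period.

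The same section promises each company "crude cumulative incidence rates of events of interest and their 95% confidence intervals for their own drugs and for the control groups". It adds that assignment implies no causal conclusion, and that multivariate analyses cannot be supplied every six months.

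Other sections show how long the second rule's window can be. Section 4: "The aim is to observe each patient for at least five years, if possible, for ten years". Section 8.1: "Patients follow up for several years will likely receive changing treatments". Section 7.2 lists lymphomas and solid malignancies among the events of interest. Section 11 ends participation at the patient's wish; neither it nor any other section ends observation at a malignancy.

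**The concern.** A long look-back for malignancies is a defensible choice, because latency is long and the responsible exposure may lie years back. That reason extends the window backwards only. It gives no ground for counting exposure that began after the diagnosis, yet the sentence as worded does not exclude it.

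At stake are the per-drug malignancy rates sent to the funding companies with confidence intervals. Section 17 lets companies use the semi-annual results for their own purposes, including internal reports and presentations. A drug that tends to be started after a cancer would carry malignancies it cannot have caused. The literal rule adds such events even if switching is unrelated to the cancer; any tendency to change treatment after a diagnosis would add more.

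**Working it through.** The protocol attaches no figure to this rule, so there is none to reproduce. The check has three parts.

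**1. The rule applied to three hypothetical patients (months from enrolment)**

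| Patient | Start of A | Start of B | Malignancy | Literal rule | With onset condition |
|---|---|---|---|---|---|
| 1 | 0 | 14 | 12 | A, B | A |
| 2 | 0 | 6 | 12 | A, B | A, B |
| 3 | – | 0 | 9 | B | B |

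Literal rule: A = 2, B = 3. With an onset condition: A = 2, B = 2. The difference is patient 1, whose cancer came two months before drug B.

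**2. Which reports can be affected**

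- *Detailed listing.* It covers events of the six-month period. A cancer at month 20 with B started at month 28 is 8 months apart, so its period closes before B begins and it does not enter B's listing. A misassignment needs B to start between diagnosis and data cut.
- *Cumulative rates.* The same cancer enters B's count only if past assignments are recomputed at each report. The protocol does not say whether they are.
- *Deaths.* No drug can start after death.

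**3. Illustrative size under no drug effect**

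None of these inputs is in the protocol; all are assumptions. Observation is T = 5 years and the first-malignancy rate is λ = 0.005 per year. Patients not enrolled on B enrol on A and start B at β = 0.10 or 0.20 per year. After a malignancy that precedes B, a proportion q = 0.2, 0.4 or 0.6 start B 6 to 12 months later.

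Per 1000 patients enrolled on A:

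- Malignancies after the start of B: a = 1000 × {β/(β+λ) × [1 − e^(−(β+λ)T)] − e^(−λT) × [1 − e^(−βT)]}
  - β = 0.20: 1000 × (0.97561 × 0.64120 − 0.97531 × 0.63212) = 9.05
  - β = 0.10: 1000 × (0.95238 × 0.40845 − 0.97531 × 0.39347) = 5.24
- Malignancies before the start of B but booked to it: e = 1000 × q × λ × ∫ e^(−(λ+β)m) G(m) dm over 0 to 5. G(m) is the chance that the delayed start still falls within observation: 1 up to year 4, falling linearly to 0 at year 4.5. Numerically e = 14.18q for β = 0.20 and 17.14q for β = 0.10.

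Per 1000 patients enrolled on B: 1000 × (1 − e^(−0.025)) = 24.69 malignancies, all after the start of B.

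Ratio of booked to proper events: (a + e)/a if nobody enrols on B; (a + 24.69 + e)/(a + 24.69) if half of the patients do.

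| β | q | e | Nobody enrols on B | Half enrol on B |
|---|---|---|---|---|
| 0.20 | 0.2 | 2.84 | 1.31 | 1.08 |
| 0.20 | 0.4 | 5.67 | 1.63 | 1.17 |
| 0.20 | 0.6 | 8.51 | 1.94 | 1.25 |
| 0.10 | 0.2 | 3.43 | 1.65 | 1.11 |
| 0.10 | 0.4 | 6.86 | 2.31 | 1.23 |
| 0.10 | 0.6 | 10.28 | 2.96 | 1.34 |

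The share of B's booked malignancies that preceded B is 1 − 1/ratio: 8% to 26% if half enrol on B, 24% to 66% if nobody does. A simulation of 2,000,000 patients per scenario agrees, and the onset-anchored rate stays at about 5 per 1000 patient-years throughout.

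For scale, 5 proper events in 1000 patient-years give 5.0 per 1000 (exact Poisson 95% CI 1.62 to 11.67). Three misassigned events make it 8.0 (3.45 to 15.76).

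**The case against.** The best defence is that the paragraph contrasts the length of the look-back, three months against unlimited, and leaves its direction unchanged. The past tense fits exposure up to the event, and the clause covers deaths too, for which only prior exposure is possible. This stands in part: practice may already stop at onset, and the protocol does not settle it. But onset is written into one rule and absent from its neighbour, and reports to several companies should not depend on a guess.

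Second, the rates follow the Manchester template, whose counting rule and denominator are not shown. This also stands. The ratios above are therefore ratios of event counts; the effect on a reported rate depends on a denominator the reader cannot see.

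Third, section 7.4 disclaims causality, and section 8.1 says that crude comparisons cannot be interpreted adequately and that treatment changes must be taken into account. These limit interpretation but do not correct a count. The section 8.1 principles are headed as applying to publications.

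A reader might infer three stronger things that the protocol does not support:

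- *That every report after the later drug starts will carry the cancer.* The detailed listing is confined to its six-month period, and refreshing of the cumulative assignments is not stated.
- *That counts are inflated two- to threefold.* This needs a drug on which nobody enrols. Section 5 enrols patients as they start an index drug, and section 14 aims for at least 500 under each.
- *That index drugs are disadvantaged against controls.* The rule covers all treatments, so a control therapy started after a cancer is charged too. The direction of a comparison is not determined.

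**Conclusion.** The point holds as a defect in the wording of a stated rule. Followed literally, the rule gives a wrong count for malignancies, and no other section restores the onset limit. The direction for any one treatment is certain: events can only be added to treatments started after the diagnosis.

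The magnitude is not derivable from the protocol. With half of the patients enrolling on the drug it is modest, about 1.1 to 1.35 times. The upper figure of about 3 marks an extreme that conflicts with the planned enrolment. Both rest on the assumed malignancy rate, switching rates and five-year observation, and on cumulative assignments being refreshed. It is not shown that any issued report is wrong. The change should be made because the rule governs recurring safety reports and is cheap to repair.

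**What to change.** Reword the sentence in section 7.4 along these lines: *each malignancy or death is assigned to every treatment the patient received under observation in the register at any time before the onset (first diagnosis) of that malignancy, or before the date of death.* State that a drug's person-time for the malignancy rate starts at its first use.

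Apply the condition to each malignancy's own onset date. A new second malignancy arising on a later drug is then still assigned to that drug, and patients with an earlier malignancy need not be excluded.

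The cost is one clause and one date comparison in the reporting program. Onset and treatment dates are already needed for the three-month rule. If practice already stops at onset, no count changes. If not, some cumulative malignancy counts already issued may be revised downward, and the next report should explain this.

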## **8. Statistical analysis**

### **8.1. Safety endpoints**

One aim of RABBIT-SpA is to protect future patients from harm caused by serious adverse events. It is impossible to achieve this aim by following a pre-specified list of primary hypotheses since the spectrum of possible SAEs is wide and every list would therefore be incomplete. New scientific results or new agents may lead to extensions and/or changes in the list of “events of interest”. Therefore, the principal investigators and the study physician are free to decide which safety concern will be investigated next.

There is no general statistical analysis plan which would be appropriate for the different scientific questions. For different AEs different confounders have to be considered. Patients follow up for several years will likely receive changing treatments. These changes have to be taken into account. Furthermore, the decision to prescribe, to stop or to continue a treatment depends on the availability of treatment options and experiences with these alternatives. For this reason the mix of patients receiving a particular treatment may change during follow-up. The risk of developing an AE may therefore change over time for various reasons (see below). Possible confounding factors or biases have to be taken into account to avoid any false conclusion. In RABBIT-SpA this will be done by considering the following principles of statistical safety analyses:

Principles of the statistical analysis for publications

a) Confounding by indication will be taken into account

Treatment decisions are based on the needs of a particular patient. Patients treated with new targeted therapies (index treatments) will be more severely ill and have more treatment failures than patients treated with standard therapies. For this reason comparisons based on crude unadjusted estimates cannot be interpreted adequately. In all publications from RABBIT-SpA appropriate statistical methods that are able to account for confounding by indication have to be applied.

b) Patient characteristics which likely influence the risk of developing a particular AE will be taken into account.

Examples for these patient characteristics are age, sex, body mass index (e.g. for cardiac disorders), co-morbid conditions (e.g. COPD), treatment history of specific drugs (e.g. glucocorticoids or NSAIDs for cardiovascular events). In the first step those risk factors will be considered for which the increased risk was shown in previous studies. Further patient characteristics which possibly influence the risk of developing the AE will be investigated in addition.

c) The possible influence of co-medication will be considered.

This applies especially, but is not limited to, treatment with glucocorticoids, NSAIDs and csDMARDs.

- d) Changing risks over time will be considered. They may result from:
- Changes in treatment
  - Selection processes caused by treatment decisions
  - Attrition: Patients who remain on a drug for more than one year are likely different from the total sample of patients in whom the treatment with this drug was started.
  - The course of the rheumatic disease itself
  - The risk of developing an AE may be influenced by the inflammatory activity (e. g. the risk of developing atherosclerosis) or other disease-related factors
- e) Power considerations needs to be conducted prior to the comparison of incidence rates
- f) Appropriate statistical methods will be applied to deal with these challenges.

Examples are (fields of application in parentheses):

- Propensity score methods [25] (confounding by indication)
  - Cox regression [26] (confounders, changing risks)
  - Generalized regression models for survival data [27-29] (confounders, changing risks, recurrent AEs)
  - Generalized estimation equations [30] (confounders, changing risks, recurrent AEs)
  - Competing risk models [31] (competing risks, selection processes)
  - Missing data models, imputation methods [32] (missing data).
- g) In the case of rare events the advantages of nested case control studies will be taken into account.
- With the availability of a large number of possible controls it should be possible to match cases who suffered from a particular SAE with controls who were similar to the cases according to a rather large number of possible confounders (up to 10).
- h) The STROBE (Strengthening the Reporting of Observational Studies in Epidemiology) guideline [33] as well as the EULAR points to consider [34] will be followed when results are published.
- Furthermore, the results will be presented in a comprehensible way to enable the reader to follow them in detail. Papers published by the RABBIT team give examples how such analyses will be performed [35-44].

To support treatment decisions, the safety analyses will focus on investigations of the risk of individual patients rather than “average patients”. This approach therefore goes beyond the traditional approach in randomized clinical trials. Interactions between disease activity, risk factors of an individual patient and the treatments applied will be considered and relative and absolute risks will be calculated. One example for this kind of approach is the development of the RABBIT risk score for serious infections. For the diseases considered here an additional ascertainment of over the counter drugs (e.g. NSAIDs) and drug compliance is needed and for that reason included in the patient e-CRFs.

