### Flow chart of parameters investigated

	ax-SpA	PsA	Study entry	At 3 months	Frequency of f/u
Physician					
Inclusion criteria	x	x	x		
Demographics (year of birth, gender)	x	x	x		
Diagnosis/disease duration/1st symptoms	x	x	x		
Health insurance	x	x	x		
Diagnostic symptoms/ASAS criteria	x		x		
Chronic inflammatory back pain	x		x		
CASPAR-classification		x	x		
Type of PsA manifestation		x	x		Every 12 months
Imaging – radiographic findings	x	x	x		Every 12 months
Physician global disease activity	x	x	x	x	Every 6 months
Height	x	x	x		
Weight	x	x	x		Every 12 months
Extent (hip, waist)	x	x	x		Every 12 months
CRP	x	x	x	x	Every 6 months

BSG		x	x	x	Every 6 months
HLA-B27	x	x	x		Every 12 months
RF / ACPA		x	x		Every 12 months
Lumbal lateralflexion	x		x		Every 12 months
Schober	x		x		Every 12 months
Arthritis (joint counts)	x	x	x	x	Every 6 months
Enthesitis	x	x	x	x	Every 6 months
Coxitis	x		x		
Joint replacements	x	x	x		Every 12 months
Vaccination	x	x	x		Every 12 months
Extraarticular manifestations	x	x	x	x	Every 6 months
Comorbidity/comedication	x	x	x		Every 12 months
Current therapy for SpA/PsA (systemic and topic)	x	x	x	x	Every 6 months
Glucocorticoids (systemic and local injections)	x	x	x	x	Every 6 months
Other therapies	x	x	x	x	Every 6 months
Previous therapies	x	x	x		
% body surface affected by psoriasis		x	x	x	Every 6 months
Pregnancy	x	x			Every 12 months
Adverse events	x	x		x	Every 6 months
Patient					
Patient global health status (NRS)	x	x	x	x	Every 6 months
Patient global disease activity (NRS)	x	x	x	x	Every 6 months
Sleep disturbances (NRS)	x	x	x	x	Every 6 months
BASDAI/BASFI	x		x	x	Every 6 months
ASAS HI	x		x		Every 12 months
HAQ/PSAID		x	x	x	Every 6 months
DLQI		x	x		Every 12 months
WHO-5	x	x	x		Every 12 months
PASS	x	x	x		Every 12 months
Patient satisfaction	x	x	x		Every 12 months
Smoking status	x	x	x		
Currently smoking	x	x	x		
Physical therapy	x	x	x		Every 12 months
Sport	x	x	x		Every 12 months
Level of education	x	x	x		
Work status	x	x	x		Every 12 months
Sick leave / Physician contacts / hospital admissions	x	x	x		Every 6 months
Work activity index (modified WAI)	x	x	x		Every 12 months
Adherence to prescribed medication	x	x	x		Every 12 months
Patient organisation	x	x	x		

Radiographs and MRIs will be uploaded at baseline and at follow-up, if available.

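### Smoking is scheduled at entry only in a 5 to 10 year cohort, and the flow chart has no row for the over-the-counter drug item that Section 8.1 places in the patient e-CRF

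*Protocol*

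**What the plan says.** **Smoking.** In the patient block of the flow chart (Protocol, Section 6), "Smoking status" and "Currently smoking" are each marked at study entry. Their month-3 and follow-up cells are empty.

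**Over-the-counter drugs.** At the end of its safety principles, Section 8.1 says that "additional ascertainment of over the counter drugs (e.g. NSAIDs) and drug compliance is needed and for that reason included in the patient e-CRFs". The patient block contains "Adherence to prescribed medication", at entry and every 12 months. No row refers to over-the-counter drugs, self-medication or NSAIDs.

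**Physician-reported drugs.** The physician block records current SpA/PsA therapy at entry, month 3 and every 6 months, and "Comorbidity/comedication" at entry and every 12 months.

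**Context.** Section 4 plans at least five years of observation per patient and ten if possible. Section 7.2 lists myocardial infarction, stroke, neoplasms and interstitial lung disease as events of interest. Section 8.1 expects treatments to change during follow-up, provides for nested case-control studies of rare events, and says of co-medication: "This applies especially, but is not limited to, treatment with glucocorticoids, NSAIDs and csDMARDs".

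**The concern.** The point has two separate parts.

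The first is a design weakness. Smoking is a plausible confounder for several listed events, and its only scheduled value dates from enrolment. For the treatment started at enrolment, that is a proper baseline. For a drug started in year 4 it is four years old. A control matched to a case late in follow-up would be matched on smoking at entry, not near the matching date. If smoking habits change differently among patients who move to different drugs, adjustment for the entry value leaves some confounding behind. No later analysis can supply values that were not asked for.

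The second is a mismatch between text and chart. Section 8.1 calls over-the-counter ascertainment necessary and places it in the patient form, yet the schedule of patient items does not show it. NSAIDs matter here: Section 5 counts them as systemic standard therapy, a relevant NSAID dose increase is a route into the control group, and Section 8.1 names them as a risk factor for cardiovascular events. Anyone working from the chart cannot tell whether or how often self-bought use is asked about.

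**Working it through.** The protocol gives no figure to reproduce on this point. The check compares the text with the flow chart and counts visits. Two illustrations on assumed inputs follow.

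**Visits (Section 4).** Baseline and months 3, 6, 12, 18, 24, 30, 36, 42, 48, 54 and 60 make 12 visits. Months 66 to 120 in six-month steps add 10, giving 22.
- Smoking as charted: 1 of 12, or 1 of 22.
- Current smoking every 12 months: 1 + 5 = 6 of 12, or 1 + 10 = 11 of 22.
- Over-the-counter use as a charted patient item: 0 of 12, or 0 of 22.

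**Text against chart.** The Section 8.1 sentence promises two things in the patient form.
- Drug compliance has a row, and that half is met. The row covers prescribed medication, so it cannot stand in for the other half.
- Over-the-counter drugs have no row, although the chart lists items as minor as sport and membership of a patient organisation.

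**Smoking cells.** Table cells can be lost when a PDF is read as text. However, height and level of education show the same entry-only pattern, so the blanks are plausibly real.

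**Illustration 1: stale smoking values.** Assume a constant share q of baseline smokers quits each year, with no relapse and no uptake. The share of baseline smokers with a wrong current status after t years is 1 − (1 − q)^t. The range q = 3-8% is an assumption, not a protocol figure.
- t = 4: 1 − 0.97^4 = 0.11; 1 − 0.92^4 = 0.28.
- t = 5: 1 − 0.97^5 = 0.14; 1 − 0.92^5 = 0.34.
- t = 10: 1 − 0.97^10 = 0.26; 1 − 0.92^10 = 0.57.

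These are misclassified shares, not bias in a drug comparison. The bias depends on how quitting differs between treatment groups, and the protocol gives nothing on that.

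**Illustration 2: unrecorded self-bought NSAIDs.** Let p be the prevalence of wholly unrecorded use in each group and RR its effect on the event. With no true drug effect, the apparent ratio is (1 + p_index(RR − 1)) / (1 + p_control(RR − 1)). Assume p of 15% (index) and 30% (control).
- RR 2: 1.15/1.30 = 0.88. RR 3: 1.30/1.60 = 0.81. RR 4: 1.45/1.90 = 0.76.
- Prevalences reversed: 1.13, 1.23 and 1.31.

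All inputs are assumed. The result can go either way, and it applies only if the difference in use is a confounder and not a consequence of the drug.

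**The case against.** A reader might infer that key confounders go unmeasured. The documents do not support that, for these reasons.

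- **Smoking is measured.** Inclusion is tied to a treatment start (Section 1), so the entry value precedes or coincides with the first exposure and can be adjusted for. The protocol nowhere promises repeated smoking data, and Section 8.1 does not name smoking among the sources of changing risk. Entry-only recording contradicts nothing.
- **The e-CRF is not shown.** The only direct statement about it, in Section 8.1, is that the over-the-counter item is in it. A missing chart heading does not prove a missing question. The chart also schedules HLA-B27, a fixed marker, every 12 months, so it may not be an exact record of item frequency.
- **NSAID use known to the physician is recorded.** NSAIDs are systemic standard therapy, and neither the six-monthly therapy row nor the annual co-medication row is limited to prescribed drugs. Only self-bought use unknown to the physician is at risk.
- **The protocol's NSAID link is narrower than it may seem.** Section 8.1 ties NSAIDs to cardiovascular events and to co-medication in general. It does not tie them to gastrointestinal or renal events.
- **NSAID reduction may be a treatment effect.** Section 1 mentions it as a possible benefit. Fewer events through that route belong to the drug's total effect, and plain time-updated adjustment could remove a real benefit.

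All of this stands, and it limits the claim. It does not settle what value to use for a drug started years after enrolment or for a late matching date; the schedule has none. Nor does it remove the mismatch on over-the-counter drugs: Section 8.1 asks for ascertainment beyond the physician rows, which already exist.

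**Conclusion.** Both parts hold, each in a limited form. Smoking is scheduled once in five to ten years, so it is out of date for later treatment episodes and for nested case-control matching. The consequence is possible residual confounding for events such as infarction, stroke, neoplasms and interstitial lung disease. This is an avoidable design weakness and not an internal contradiction. On over-the-counter drugs, Section 8.1 and the flow chart disagree and must be reconciled; it is not established that the data are not collected.

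The size is not known from the documents. The misclassified shares (14-34% at five years, 26-57% at ten) and the distorted ratios (0.76-0.88, or 1.13-1.31 reversed) rest entirely on assumed quit rates, prevalences and risk ratios. They show what could happen, not what is expected. The entry-only reading also assumes that the blank smoking cells are blank in the original table.

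**What to change.** 1. **Smoking.** Mark current smoking every 12 months in the patient questionnaire. In analysis, adjust for the latest value before the start of each treatment episode or, in nested case-control studies, before the matching date.
2. **Over-the-counter drugs.** Check the patient e-CRF. If the item exists, add its row and frequency to the flow chart. If it does not, add a short item to the existing six-monthly patient questionnaires and chart it.
3. **Use of the NSAID data.** Adjust for over-the-counter NSAID use as measured before each treatment episode, or use methods suited to time-varying confounders affected by earlier treatment. Do not enter it as an ordinary time-updated covariate when the total drug effect is the target.

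**Cost.** One short smoking question a year in an existing online form, an amended flow chart, possibly one further patient item, and an amendment for the Ethics Committee. Patient burden rises slightly. Smoking at visits already past stays missing, so analyses of earlier episodes should state how old the smoking value is.
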